1 PROTOCOL SUMMARY

1.1 SYNOPSIS

Title: A randomized, placebo-controlled crossover study to assess the safety of administering a second dose of an mRNA-based COVID-19 vaccine in individuals who experienced a systemic allergic reaction to an initial dose

Study Description: This is a single-site study to determine the safety of administering a dose of the Pfizer-BioNTech mRNA coronavirus disease 2019 (COVID-19) vaccine (Comirnaty) to individuals who experienced a systemic allergic reaction to their first full dose of the same vaccine or the Moderna mRNA vaccine, and to investigate possible mechanisms underlying allergic reactions.

Objectives:

Primary Objective:

1. Assess the proportion of participants who develop a **systemic allergic reaction** (Consortium for Food Allergy Research [CoFAR; see [Appendix A](#)] grade 2 reaction and above regardless of tryptase, or CoFAR grade 1 with elevated tryptase [1.2 X baseline plus 2ng/mL]) to the Pfizer-BioNTech COVID-19 vaccine after previously demonstrating a systemic allergic reaction (CoFAR Grade 2 or 3 reaction regardless of tryptase OR Grade 1 reaction with elevated tryptase [1.2 X baseline plus 2ng/mL]) to their first full dose of the same vaccine or the Moderna COVID-19 vaccine.

Secondary Objectives:

1. Assess the proportion of participants who develop a **severe systemic allergic reaction** (CoFAR Grade 3 reaction or higher regardless of tryptase) to the Pfizer-BioNTech COVID-19 vaccine after previously demonstrating a systemic allergic reaction (CoFAR Grade 2 or 3 reaction regardless of tryptase OR Grade 1 reaction with elevated tryptase [1.2 X baseline plus 2ng/mL]) to their first full dose of the same vaccine or the Moderna COVID-19 vaccine.
2. Assess the proportion of participants who develop a **mild-moderate allergic reaction** (CoFAR Grade 1 or 2 reaction regardless of tryptase) to the Pfizer-BioNTech COVID-19 vaccine after previously demonstrating a systemic allergic reaction (CoFAR Grade 2 or 3 reaction regardless of tryptase OR Grade 1 reaction with elevated tryptase [1.2 X baseline plus 2ng/mL]) to their first full dose of the same vaccine or the Moderna COVID-19 vaccine.

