4. Investigate mental health characteristics of participants who experience an allergic reaction to the COVID-19 vaccine.
5. Assess psychological impact of allergic reactions to the COVID-19 vaccine and examine changes in stress levels over time.
6. Assess anxiety levels in participants and examine changes in anxiety over time.
7. Assess the proportion of participants who experience no reaction or only a mild reaction (CoFAR Grade 2 or below) to a booster dose of the Pfizer-BioNTech vaccine after previously demonstrating a systemic allergic reaction (CoFAR Grade 2 or 3 reaction regardless of tryptase OR Grade 1 reaction with elevated tryptase [1.2 X baseline plus 2 ng/mL]) to their first full dose of the Pfizer-BioNTech or Moderna COVID-19 vaccine and no allergic reaction or a mild reaction (CoFAR Grade 2 or below) to a subsequent (second) dose of the Pfizer-BioNTech vaccine.
8. Assess the development of autoantibodies after COVID-19 vaccination.

Endpoints:

Primary Endpoint:

1. The proportion of participants who previously demonstrated a systemic allergic reaction (CoFAR Grade 2 or 3 reaction regardless of tryptase OR Grade 1 reaction with elevated tryptase [1.2 X baseline plus 2ng/mL]) to their first full dose of the Pfizer-BioNTech or Moderna COVID-19 vaccine who experience a **systemic allergic reaction** (CoFAR Grade 2 and above reaction regardless of tryptase, or CoFAR grade 1 with elevated tryptase [1.2 X baseline plus 2ng/mL]) within the 3-hour post-vaccine observation period to a subsequent dose of the Pfizer-BioNTech vaccine.

Secondary Endpoints:

2. The proportion of participants who previously demonstrated a systemic allergic reaction (CoFAR Grade 2 or 3 reaction regardless of tryptase OR Grade 1 reaction with elevated tryptase [1.2 X baseline plus 2ng/mL]) to their first full dose of the Pfizer-BioNTech or Moderna COVID-19 vaccine who experience a **severe systemic allergic reaction** (CoFAR grade 3 reaction and above) within the 3-hour post-vaccine observation period to a subsequent dose of the Pfizer-BioNTech vaccine.

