9. Prevalence of positive skin testing to the vaccine and/or vaccine components including PEG- and polysorbate 80-containing medications.
10. Changes in biomarkers from baseline to post-dose of the Pfizer-BioNTech vaccine administered on study (e.g., known mediators of systemic reactions due to mast cell activation, markers of inflammatory response, markers of basophil and neutrophil activation, markers associated with activation of the classical and alternative complement pathways or kinin system, proteomics, metabolomics).
11. Changes in blood transcriptomics after vaccination.
12. Changes in innate and adaptive immune responses including functional antibody levels after vaccination.
13. Mental health/anxiety questionnaire scores and anxiety level ratings at baseline.
14. Results of psychiatric consultation/mental health interview.
15. Changes in mental health/anxiety questionnaire scores and anxiety level ratings over the study period.
16. The proportion of participants who previously demonstrated a systemic allergic reaction (CoFAR Grade 2 or 3 reaction regardless of tryptase OR Grade 1 reaction with elevated tryptase [1.2 X baseline plus 2 ng/mL]) to their first full dose of the Pfizer-BioNTech or Moderna COVID-19 vaccine and no allergic reaction or a mild reaction (CoFAR Grade 2 or below) to a subsequent (second) dose of the Pfizer-BioNTech vaccine who experience no reaction or only a mild reaction (CoFAR Grade 2 or below) to a booster dose of the Pfizer-BioNTech vaccine administered approximately 5 months after the second dose.
17. The development of autoantibodies post-second and post-booster doses of the COVID-19 mRNA vaccines.

Study Population:	Up to 100 male and female participants ages 16-69 years of age who experienced a systemic allergic reaction (CoFAR Grade 2 or 3 reaction regardless of tryptase OR Grade 1 reaction with elevated tryptase [1.2 X baseline plus 2 ng/mL]) after receiving their first dose of the Pfizer-BioNTech or Moderna COVID-19 vaccine.
Phase:	N/A
Description of Sites/Facilities	This is a single site study; all participants will be enrolled at the NIH Clinical Center.
Enrolling Participants:	
Description of Study Intervention:	Participants who experienced a systemic allergic reaction after receiving their first full dose of the Pfizer-BioNTech or Moderna COVID-19 vaccine will be enrolled and receive a subsequent dose of the Pfizer-BioNTech vaccine and placebo in a randomized order on consecutive days.

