8.2.2 Biospecimen Evaluations

Specimens (blood, urine, and nasal swabs) will be used to assess:

- Overall atopic status
- Pre-existing antibodies to polyethylene glycols (Sample analysis will not be completed prior to vaccination; therefore, results will not be used to assess eligibility.)
- Known mediators of systemic reactions due to mast cell activation (e.g., serum tryptase and urinary leukotrienes, prostaglandins, histamine)
- General markers of an acute inflammatory response (e.g., serum IL-6)
- Activation of the classical and alternative complement pathways
- Contact activation of the kinin system
- Activation of basophils and neutrophils
- Unsupervised proteomics, metabolomics, and whole blood transcriptomics
- Analysis of peripheral blood mononuclear cells (PBMCs) may also be explored to assess for new mechanisms
- Evidence of clonal mast cell disease and genetic variants that may increase the risk and/or severity of allergic reactions (e.g. hereditary alpha tryptasemia, clonal mast cell disease)
- Autoantibodies pre and post COVID-19 vaccination

Specific laboratory studies may include those listed below. Assays may be removed or added based on the number and character of reactions seen within the trial. In addition, the timepoints for the conduct of specific laboratory studies may change from what is specified below.

Specimens will be processed at the Laboratory of Allergic Diseases (LAD), Laboratory of Viral Diseases (LVD), Laboratory of Immune System Biology (LISB), and the Laboratory of Bacteriology at the Rocky Mountain Laboratories at NIAID, the Department of Laboratory Medicine (DLM) at NIH (including send-outs to Mayo Clinic), and the Systemic Autoimmunity Branch at the National Institute of Arthritis and Musculoskeletal and Skin Diseases. Coded specimens will also be sent to collaborators at Yale University, Virginia Commonwealth University, Stanford University, University of North Carolina, University of Pittsburgh, KalVista Pharmaceuticals, Inc., and the US FDA for processing.

Blood/serum/plasma:

The following tests may be performed for all participants:

- Whole blood for genetic analysis of the tryptase locus, c-kit locus, and other genetic variants that might influence the risk and/or severity of allergic reactions (Visit 1, pre-dosing)
- Total IgE (Visit 1, pre-dosing Day 1 only)
- Allergen-specific IgE (Visit 1, pre-dosing)

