9.4 STATISTICAL ANALYSES

9.4.1 General Approach

Most analyses will result in estimates of binary endpoints and will be presented as proportions and corresponding exact 95% confidence intervals.

Exploratory endpoints, such as mechanistic endpoints, will be presented as means with standard deviations and/or as medians and interquartile ranges. Graphical presentation may be useful.

While hypothesis testing is likely to be limited in scope, two-sided p-values with alpha=.05 will be used, with appropriate cautions regarding interpretation due to multiplicity.

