9.4.9 Exploratory Analyses

Baseline mechanistic endpoints and other potential risk factors including results of mental health and anxiety assessments as well as changes in these endpoints pre- and post-vaccine will be described and compared between those with and without systemic allergic reactions (and likewise for other allergic endpoints). Analyses will generally use Wilcoxon rank sum tests when comparing groups and signed rank tests when comparing within subjects (e.g., pre- versus post-vaccine), however parametric tests might be used if number of enrolled patients is sufficient.

The ability to do hypothesis testing and modelling of risk factors and changes in exploratory endpoints pre- and post-vaccine will depend on the number of subjects enrolled. The proportion of subjects who react to the study-administered booster dose (among those who receive it), will be computed along with the corresponding 95% confidence interval, using the Clopper-Pearson method.

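### For serum tryptase, the Section 9.4.9 comparison of reactors with non-reactors is partly circular, because a Grade 1 case counts as a reaction only if tryptase rose

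*Combined protocol and SAP*

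**What the plan says.** - **Grouping.** The primary endpoint (Section 1.1) counts CoFAR Grade 2 or higher whatever the tryptase, and also "CoFAR grade 1 with elevated tryptase [1.2 X baseline plus 2ng/mL]) within the 3-hour post-vaccine observation period". Grade 1 symptoms without the rise are not a systemic reaction.
- **Outcome.** The exploratory endpoints in Section 1.1 include change from baseline to post-dose in biomarkers such as "known mediators of systemic reactions due to mast cell activation". Section 8.2.2 gives the examples: "Known mediators of systemic reactions due to mast cell activation (e.g., serum tryptase and urinary leukotrienes, prostaglandins, histamine"). Tryptase may be drawn before each study injection and at 35 minutes and 2 hours after it.
- **Comparison.** Section 9.4.9 covers baseline mechanistic endpoints and their changes from before to after vaccine, which "will be described and compared between those with and without systemic allergic reactions (and likewise for other allergic endpoints"). On method: "Analyses will generally use Wilcoxon rank sum tests when comparing groups". Section 9.4.1 sets the level: "two-sided p-values with alpha=.05 will be used, with appropriate cautions regarding interpretation due to multiplicity".
- **Exceptions.** None of these sections exempts tryptase or gives a tryptase-free grouping for it. Section 9 says no formal SAP is intended, so no later document is planned that would settle this.

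**The concern.** Among Grade 1 participants, the tryptase change alone decides the group. Those with a rise go to the reactors and those without go to the non-reactors. Comparing tryptase change between the two groups then returns, in part, the rule used to form them. A difference is expected even if tryptase has nothing to do with symptoms.

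The protocol wants to understand mechanism and recognises that anxiety can mimic anaphylaxis (Sections 2.2 and 4.2). Appendix A lists flushing and nausea as Grade 1 symptoms. Section 2.2 lists flushing among the features of conditions that mimic anaphylaxis, and Section 8.3 lists nausea as an expected vaccine effect. Non-allergic Grade 1 cases are therefore plausible, and these are the cases that tryptase sorts. A significant tryptase difference could be reported as evidence of mast-cell activation when part of it restates the case definition.

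**Working it through.** **Inputs from the documents.** The reaction definition, the rank-sum test, two-sided alpha 0.05, and N up to 100 but possibly much smaller (Section 9.2).

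**Assumptions, not in the documents.** Let g1 be the share with Grade 1, g2 the share with Grade 2 or higher, and q the share crossing the tryptase threshold independently of symptoms. Three mixes (g1/g2) are used: 15/5, 20/20 and 40/20 percent. The first matches the only symptom rate given, 20% with potentially allergic symptoms at the second dose (Section 2.3.3).

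**Step 1: the plan's nominal level.** With groups formed by symptoms alone and tryptase independent of grade, simulation (40,000 trials per cell) gives rejection rates at N=100 of 0.043-0.052 for Grade 2 or higher versus lower, and 0.048-0.051 for any grade versus none. At N=16 to 40 both are at or below 0.05. The nominal 5% holds.

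**Step 2: the bias by arithmetic.** Under the plan's definition:
- P(reactor) = g2 + g1 q
- P(rise | reactor) = (g1 + g2) q / (g2 + g1 q)
- P(rise | non-reactor) = (1 - g1 - g2) q / (1 - g2 - g1 q)

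For 40/20 and q = 0.10: P(reactor) = 0.20 + 0.04 = 0.24; rise among reactors 0.06/0.24 = 25.0%; rise among non-reactors 0.04/0.76 = 5.3%. The gap is 19.7 percentage points with no true association.

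| g1/g2 | q | Rise, reactors | Rise, non-reactors | Gap (points) |
|---|---|---|---|---|
| 15/5 | 1% | 3.9% | 0.8% | 3.0 |
| 15/5 | 10% | 30.8% | 8.6% | 22.2 |
| 20/20 | 1% | 2.0% | 0.8% | 1.2 |
| 20/20 | 10% | 18.2% | 7.7% | 10.5 |
| 40/20 | 1% | 2.9% | 0.5% | 2.4 |
| 40/20 | 10% | 25.0% | 5.3% | 19.7 |

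**Step 3: rejection rate of the nominal 5% rank-sum test under the plan's grouping.** The rise is measured on the scale of the threshold.

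| g1/g2 | q | N=20 | N=40 | N=100 |
|---|---|---|---|---|
| 15/5 | 1% | 0.009 | 0.030 | 0.054 |
| 15/5 | 5% | 0.018 | 0.054 | 0.104 |
| 15/5 | 10% | 0.033 | 0.093 | 0.183 |
| 20/20 | 1% | 0.036 | 0.049 | 0.053 |
| 20/20 | 5% | 0.044 | 0.061 | 0.075 |
| 20/20 | 10% | 0.057 | 0.084 | 0.128 |
| 40/20 | 1% | 0.041 | 0.058 | 0.055 |
| 40/20 | 5% | 0.062 | 0.084 | 0.138 |
| 40/20 | 10% | 0.09-0.12 | 0.15 | 0.31-0.32 |

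The first two mixes use 40,000 trials per cell, except 20/20 at 1% and N=20, which uses 4,000. The 40/20 cells at 1% and 5% also use 4,000. Ranges in the last row are separate runs of the same setting.

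**Step 4: other scales and mediators.** These use 40/20, q = 10% and 1,500 trials per cell. A test on absolute tryptase change rejects 0.13 at N=40 and 0.27 at N=100. A mediator correlated 0.6 with tryptase rejects 0.10 and 0.16. The bias carries over, but weakens.

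**The case against.** The case on the other side has several sound parts.

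- Section 9.4.9 does not name tryptase, and Section 8.2.2 lets assays be added or removed. The comparison follows from reading the sections together; it is not a named test.
- Tryptase-free contrasts are already planned through the extension to other allergic endpoints: Grade 3 or higher, and Grade 1-2 regardless of tryptase. Section 9.4.9 also plans within-person signed-rank tests, which need no reactor grouping, and tryptase is drawn after placebo as well. The mechanistic question does not rest on this contrast alone.
- The analysis is exploratory, testing depends on enrolment, and Section 9 puts estimation and description first.
- How often tryptase crosses the threshold for unrelated reasons is unknown. At an assumed baseline of 5 ng/mL the threshold is 1.2 x 5 + 2 = 8 ng/mL, a 60% rise. If such crossings are about 1%, the excess is negligible.

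All of this limits the size and the stakes. It does not remove the circularity: the tryptase-free contrasts sit beside the circular one and do not replace it. Small N keeps the rejection rate low but leaves the descriptive gap of Step 2 in place.

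A reader might infer that the test misleads in a third or more of trials. Rates of 33-49% at N=40 and 67-87% at N=100 do arise with 40% Grade 1, 20% Grade 2 or higher and a symptom-unrelated rise in 20-30% of people. The documents support none of those inputs. A reader might also infer that the Brighton anaphylaxis comparison is distorted to a similar degree. Appendix B does list tryptase, but as one minor criterion with a different threshold, and it cannot make a case without a cardiovascular or respiratory criterion. No size has been shown for that effect.

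**Conclusion.** The concern holds in a limited form. Followed as written, 9.4.9 gives a tryptase contrast that is biased toward a difference by the reaction definition itself, with a weaker effect on correlated mediators. If the rise is unrelated to symptoms and the grade mix lies in the assumed range, a 10% rise rate gives rejection of about 3-12% at N=20, 8-15% at N=40 and 13-31% at N=100. A 1% rise rate gives about 3-6% at N=40 and 5-6% at N=100, which is essentially nominal. The direction follows from the definitions; the size rests on assumptions.

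A reader might take this as a flaw in the trial's main results. The documents do not support that: the primary and secondary endpoints do not use this comparison, and keeping tryptase in their definitions is not questioned here.

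**What to change.** Add to Section 9.4.9: *For tryptase and other mast-cell mediators, participants are grouped by CoFAR symptom grade alone (Grade 2 or higher versus lower, and any grade versus none), and the Brighton level is derived without its laboratory criterion. Any comparison of tryptase by the tryptase-containing reaction definition is shown descriptively, without a p-value.* Keep the existing definitions for the primary and secondary endpoints and for markers not linked to tryptase.

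This needs no new data if grade and tryptase are held as separate items. The cost is that the grouping for these mediators differs slightly from the primary endpoint. Section 4.1 reports only 2 participants still to complete the 5-month visit in September 2022, so the change may come after most Visit 1 data exist. In that case, date and disclose it, or at the least state the circularity wherever the tryptase contrast is reported.

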Prior to enrollment, participants will be screened remotely by phone/email and/or videoconference (using an NIH-approved platform) to assess eligibility and to ensure co-morbid allergic and other diseases, including asthma and atopic dermatitis, are well-controlled and disease activity is stable. If individuals have co-morbid conditions that may increase their risk of having a severe allergic reaction, they may be asked to come to the NIH CC for additional studies, such as pulmonary function testing, echocardiogram, or blood laboratory testing, that are felt to be clinically necessary (based on the discretion of the study team) to ensure that they are medically stable to undergo the study intervention. After screening, eligible individuals will be enrolled and admitted to the NIH CC ICU on day 0. Two IV lines will be inserted prior to study vaccination to allow for frequent blood draws and rapid administration of fluids/medications if needed in the event of a reaction. We will aim to admit subjects so that their first study vaccination occurs as close as possible to when the second dose of vaccine is indicated (i.e., 21 days after the first dose of the Pfizer-BioNTech vaccine and 28 days after the first dose of the Moderna vaccine), but since the goal of this study is to assess allergic reactions and not provide clinical vaccinations as indicated, subjects may be enrolled regardless of time elapsed since their initial vaccination. On day 1, they will be randomized at a 1:1 ratio to receive either placebo or the Pfizer-BioNTech vaccine. A pre-vaccination blood and urine sample will be obtained, and then the first dose (per randomization) of study vaccine will be given. Serial blood draws and the first void (urine) after the dose will be collected. Another post-vaccination void may be collected if an allergic reaction occurs after the first collection. The participant will be monitored by the principal investigator and/or an experienced allergist associate investigator for signs and symptoms of an allergic reaction and any other AE for a minimum of 3 hours, and medications and equipment will be immediately available to treat possible reactions. If a reaction does develop, the participant will be treated according to our study MOP, and additional urine samples may be collected to assess the immune response. If a skin rash develops, photographs may be taken to document variations in presentation. In case of a reaction after the first dose, the participant will be counseled and the second study vaccination will proceed as scheduled if the participant is willing. On day 2, the participant will receive either placebo or the Pfizer-BioNTech vaccine (whichever was not given on day 1) using the same procedure, but in the opposite arm. The participant will be monitored and treated (as needed) for an allergic reaction or AEs and samples will be collected as described for day 1. Participants will be discharged on day 3, unless they require additional treatment due to a reaction. Additionally, day 2 dosing may be delayed to a later day at the discretion of the investigator if the participant experiences an allergic reaction on day 1 that has not resolved by day 2 and does not rise to the level of a pausing or halting criterion (see sections 8.4.5 and 8.4.6). Day 2 dosing may be delayed for a maximum of 1 week. If the participant experiences other AEs (nonallergic in nature) on day 2 that are expected from the vaccine based on data from the Phase 3 trials (e.g. fatigue, headache, fever, myalgia), then the second study vaccination may still be given on day 2 as scheduled. A participant may be moved to a general ward after the completion of their vaccinations and close monitoring, when safe to do so.

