6.5 CONCOMITANT THERAPY

The following medications are prohibited during participation in the study:

- Systemic immunomodulators including systemic steroids.
- Biologic agents that will interfere with the study objectives at the discretion of the investigator.
- EUA monoclonal antibodies casirivimab and indevimab, or bamlanivimab, or any COVID-19-specific biologic including antibodies or immunomodulator for at least 5 half-lives.
- Zileuton.
- Any investigational or approved vaccines administered outside of the study prior to visit 3 and, for participants receiving a booster vaccination at visit 4, at least 2 months before visit 4 through visit 6.
- Any allergen immunotherapy administration within 24 hours prior to the first study vaccination through 24 hours after the second study vaccination, and from 24 hours prior to through 24 hours after visit 4 (for participants receiving the booster vaccination).

Since one of the goals of this study is to understand the mechanisms of allergic reactions to the COVID-19 vaccines, these medications have been excluded since they may interfere with analysis in mechanistic studies.

Participants may be asked to discontinue use of antihistamines and drugs with antihistamine properties prior to the study intervention as well as prior to skin testing at visit 3 or 4 and booster vaccination at Visit 4 (as applicable) since these medications can mask signs and symptoms of an allergic reaction, thereby reducing the accuracy of skin testing and affecting results of research tests following the booster vaccination. Participants will be asked to discontinue these medications for a time period equal to at least 5 half-lives of the medication prior to the study

intervention.^[31] These medications can be resumed once the participant is discharged at the end of Visit 1 and after Visit 3 or 4.

Unless medically contraindicated, participants may also be asked to discontinue use of beta blockers, ACE inhibitors, and NSAIDS that are thought to interfere with treatment of allergic reactions or that may act as eliciting factors that increase reactivity in susceptible individuals^[31] for a time period of 5 half-lives of the medication prior to the vaccine challenge at Visit 1 and the booster vaccination at Visit 4 (as applicable). They can resume these medications once they complete the study interventions at the respective visit.

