- Anti-Polyethylene glycol (PEG) IgE, IgG, and IgM antibody measurements (Visit 1, pre-dosing, and Visits 3, 4, and 6)
- Anti-SARS-CoV-2 antibodies and functional antibodies (Visit 1, pre-dosing, and Visits 3, 4, and 6)
- Serum total and mature tryptase (Visit 1, pre-dosing, and post-dosing (placebo and vaccine) at 35 minutes and 2 hours)
- Complement activation testing (Visit 1, pre-dosing, and post-dosing (placebo and vaccine) at 35 minutes and 2 hours)
- Flow cytometry for immunophenotyping and assessment of immune activation (Visit 1, pre-dosing, and post-dosing (placebo and vaccine) at 35 minutes, 2 hours, 6 hours, and 24 hours; and Visits 3, 4, and 6)
- Flow cytometry and other assays to assess basophil and neutrophil activation (Visit 1, pre-dosing, and post-dosing (placebo and vaccine) at 35 minutes and 2 hours)
- CBC with differential (Visit 1, pre-dosing, and post-dosing (placebo and vaccine) at 35 minutes, 2 hours, 6 hours, and 24 hours; and Visits 3, 4, and 6)
- Whole blood and single cell transcriptomics and/or CITE-seq (Visit 1, pre-dosing, and post-dosing (placebo and vaccine) at 35 minutes, 2 hours, 6 hours, and 24 hours; and Visits 3, 4, and 6)
- Plasma proteomics and metabolomics (Visit 1, pre-dosing, and post-dosing (placebo and vaccine) at 35 minutes, 2 hours, 6 hours, and 24 hours; and Visits 3, 4, and 6)
- PBMC separation and storage (Visit 1, pre-dosing, and post-dosing (placebo and vaccine) at 35 minutes, 2 hours, 6 hours, and 24 hours; and Visits 3, 4, and 6)
- Plasma Kallikrein (Visit 1, pre-dosing, and post-dosing (placebo and vaccine) at 35 minutes and 2 hours)
- Measurement of platelet activating factor (PAF) and platelet activating factor acetylhydrolase (PAF-AH) as well as neutrophil nets (Visit 1, pre-dosing, and post-dosing (placebo and vaccine) at 35 minutes and 2 hours)
- Serum cortisol level (Visit 1, pre-dosing, and post-dosing (placebo and vaccine) at 35 minutes and 2 hours)
- Metanephrine/normetanephrine (Visit 1, pre-dosing, and post-dosing (placebo and vaccine) at 35 minutes and 2 hours)
- Autoantibody levels (Visit 1, pre-dosing; Visit 3, Visit 4, pre-dosing; and Visit 6)
- Serum pregnancy test for participants of childbearing potential (Visit 1 prior to study intervention)

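### The biomarker endpoint and its one named within-subject test use vaccine-phase change alone, although matched placebo-phase samples are taken; handling of samples drawn after treatment of a reaction is not stated

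*Combined protocol and SAP*

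**What the plan says.** **Endpoint.** The biomarker endpoint (section 1.1, exploratory endpoint 10; section 3, exploratory endpoint 4) is change from baseline to after the Pfizer-BioNTech dose given on study. Placebo is not part of the definition.

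**Tests.** Section 9.4.9 will in general use rank sum tests between groups and "signed rank tests when comparing within subjects (e.g., pre- versus post-vaccine". It also says that baseline mechanistic measures, and their changes around vaccination, "will be described and compared between those with and without systemic allergic reactions".

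**Samples.** Section 8.2.2 collects the assays in both phases, for example "Serum cortisol level (Visit 1, pre-dosing, and post-dosing (placebo and vaccine) at 35 minutes and 2 hours" and "Metanephrine/normetanephrine (Visit 1, pre-dosing, and post-dosing (placebo and vaccine) at 35 minutes and 2 hours". Tryptase and complement follow the same pattern. Under section 8.2.1 the 24-hour draw after the Day 1 injection is also the Day 2 baseline.

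**Where the crossover is used.** Section 9.4.3 specifies a first-injection comparison and a within-subject comparison of active with placebo, but only for clinical reaction rates.

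**Treatment of reactions.** Section 4.1: "If a reaction does develop, the participant will be treated according to our study MOP". Section 6.5 says of the prohibited drugs, which include systemic steroids, that "these medications have been excluded since they may interfere with analysis in mechanistic studies".

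**No later document.** Section 9 states that no formal SAP is intended.

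**The concern.** Section 1.1 gives two purposes for the study: safety of a further dose, and the mechanism of reactions. For mechanism, the written endpoint and the one named within-subject test leave out the control that the design provides.

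Every participant is in an ICU, has repeated draws, and has reason to be anxious. Cortisol and metanephrines are obvious candidates to move under those conditions whichever syringe is given. A pre- versus post-vaccine test would credit that movement to the vaccine.

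A separate exposure arises when post-dose changes are compared between reactors and non-reactors. If some reactors were treated before a draw, the sample reflects reaction plus drug. Section 6.5 accepts that some drugs can disturb mechanistic assays, but no visible passage says how samples taken after treatment are flagged or analysed. The drug effect could create a difference or hide a real one.

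**Working it through.** The plan gives no power or precision figure for mechanistic endpoints, so there is nothing of its own to reproduce. The two exposures were examined by simulation.

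**Inputs from the protocol:** two-sided alpha 0.05 (9.4.1); rank sum and signed rank tests (9.4.9); 1:1 order (6.3); enrollment up to 100 and possibly far fewer (9.2).

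**Assumed, not in the documents:** changes are normal with SD 1, phases are independent, and the true vaccine or mechanism effect is zero. Shifts are in SDs of change. There were 1,500 runs per cell, so the Monte Carlo standard error is at most √(0.5×0.5/1500) = 1.3 percentage points.

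**1. Within-subject test under shared drift *d*.** Vaccine-phase change is V = *d* + e₁ and placebo-phase change is P = *d* + e₂. The signed rank test on V is centred on *d*; on V − P it is centred on *d* − *d* = 0.

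| N | V alone, *d* = 0.25 | V alone, *d* = 0.5 | V alone, *d* = 1 | V − P, all three |
|---|---|---|---|---|
| 10 | 10% | 30% | 78% | 4–5% |
| 20 | 17% | 54% | 99% | 5% |
| 40 | 32% | 85% | 100% | 4–5% |
| 100 | 70% | 100% | 100% | 5% |

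With *d* = 0, the test on V alone rejects 4–6%, so the problem exists only where there is drift. Where there is, a larger N makes it worse.

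**2. Reactors versus non-reactors.** A 1 SD drift common to both groups leaves the rank sum test at 4–6%; shared drift cancels. If a drug effect of 0.5 to 1 SD is added to every reactor's sample, with 20% or 40% reactors, rejection is 8–22% (N=10), 13–51% (N=20), 21–83% (N=40) and 48–100% (N=100). Treating every reactor before the draw is the extreme case; partial treatment gives less.

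**3. Limit of paired subtraction.** In the vaccine-first half, the placebo phase begins from the 24-hour post-vaccine sample. If that half carries a residual vaccine shift *c* into its placebo-phase change, V − P is centred on −*c*/2 overall. With *d* = 0.5 and no acute vaccine effect:

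| N | V − P, *c* = 0.5 | V − P, *c* = 1 | First injection only |
|---|---|---|---|
| 20 | 11% | 29% | 4–5% |
| 40 | 18% | 51% | 4–5% |
| 100 | 37% | 92% | 4–5% |

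The first-injection comparison of change uses no Day 2 data and is unaffected.

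**4. Cost in power.** With independent phases, V − P has SD √2, so a 0.75 SD effect becomes 0.75/1.414 = 0.53 SD. At N=20 with no drift, power falls from about 87% (V alone) to about 60% (V − P). Positive correlation between phases would reduce the loss.

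**The case against.** The strongest defence is that section 9.4.9 is worded openly. It says what analyses will generally use and gives pre- versus post-vaccine only as an example. A vaccine-versus-placebo signed rank test is also a within-subject comparison, and collecting placebo-phase samples suggests that someone means to use them. That stands: a reader might infer that a placebo contrast is ruled out, and it is not. But the endpoint is defined on the active dose alone, so a plan followed as written yields the uncontrolled test.

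A reader might also infer that ICU and anxiety effects distort the comparison of reactors with non-reactors. They do not when shared by both groups.

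A third tempting reading is that treated reactors are set against untreated non-reactors, so that reaction and drug are fully confounded. The documents do not support this. Section 2.3.1 says only that reactors may need medication. A systemic reaction can be Grade 2 with mild symptoms, or Grade 1 with raised tryptase, and nothing says that all of these are treated. The MOP, which governs treatment, is not in the visible material and may address samples. The antihistamine wording in section 6.5 ("thereby reducing the accuracy of skin testing and affecting results of research tests following the booster vaccination") concerns skin testing and the booster visit, not Visit 1 samples after a reaction.

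Some overlap of treatment and draws is still plausible. In the anaphylaxis reports summarised in section 2.2, 89% had onset within 30 minutes and 92% of reactions received epinephrine, while the first post-dose draw is at 35 ± 15 minutes. Those were anaphylaxis cases; milder reactors may be treated less often.

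Finally, these are exploratory analyses with a multiplicity caution (9.4.1). That limits the weight of the point, but a multiplicity caution does not address bias.

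**Conclusion.** The point holds in limited form. The biomarker endpoint and its one named within-subject test omit a control already sampled at matched times. If drift of 0.25 to 0.5 SD is shared by both phases, the pre/post test gives false positives about 17% to 54% of the time at N=20, against about 5% for vaccine minus placebo without carry-over. These figures rest on assumed drift and independent normal changes. For markers with no drift there is no inflation.

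The comparison of reactors with non-reactors is exposed only where treatment preceded a draw. How often that happens cannot be determined from the documents, so the simulated rates show what is possible rather than what is expected. Comparisons of pre-dose baseline measures are not affected, except a Day 2 baseline after a treated Day 1 reaction.

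This is worth correcting because mechanism is a stated purpose and the better contrast uses samples already scheduled. It does not touch the primary or secondary endpoints.

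**What to change.** Amend section 9.4.9 as follows.

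**(a) Vaccine effect on biomarkers.** Base claims on two placebo-referenced contrasts of equal standing:
- the randomized first-injection comparison of change, active versus placebo on Day 1, which is free of carry-over;
- the within-subject vaccine-phase minus placebo-phase change at matched times, allowing for sequence and period. Adjusting for period does not remove carry-over, which is why the first contrast must not be demoted to a check.

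Keep pre- versus post-vaccine change as description.

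**(b) Reactors versus non-reactors.** State which injection defines a reactor. Flag each post-dose sample drawn after treatment of a reaction, including Day 2 samples after a treated Day 1 reaction. Report an analysis limited to pre-treatment samples as a sensitivity analysis beside the full data. It should not replace the full data: it selects on a post-dose event and could leave the fastest reactors with no usable post-dose sample.

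**Cost.** No new samples are needed. Paired subtraction loses power if there is no drift (about 87% to 60% at N=20 for a 0.75 SD effect), and the first-injection contrast uses one phase per participant. Participants who get no second injection, such as those with a Grade 4 reaction on Day 1 (6.3, 8.4.5.2), drop out of the paired contrast. The visible text provides for concomitant-medication review but not for dose times matched to draws, so the recording of those times must be confirmed. Section 4.1 notes that by September 2022 only two participants had yet to complete the 5-month visit, and unblinding follows the last Visit 1. The change should therefore be dated and labelled as possibly made after unblinding.
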